9.1 STUDY DESIGN

This study will be a non-interventional study using existing data from January 1, 2014 to the date of the latest available data from an IQVIA (detailed below) database. Data available after March 31, 2020 will not be used due to the potential confounding events of coronavirus.

The study will analyze the clinical and economic effect of empagliflozin in Type 2 Diabetes (T2D) patients with Cardiovascular Disease (CVD). Empagliflozin initiators, as an add-on to metformin therapy comprise the treatment population. Patients initiating sulfonylureas as an add-on to metformin comprise the control population.

The index date for the empagliflozin add-on therapy arm is defined as the date of initiation of empagliflozin.

Treatment patient: Empagliflozin + Metformin
Control patient: Sulfonylurea + Metformin
 Metformin initiation Index Date = Empagliflozin/Sulfonlurea initiation

Page 16 of 36

The index date for the sulfonylurea add-on therapy control arm in a format parallel to the definition for the empagliflozin add-on therapy treatment arm, i.e., the index date is defined as the date of initiation of sulfonylurea therapy. We will control for exposure time in our propensity score calculations.

Baseline characteristics for all patients as well as their enrollment status will be confirmed using 12 months of claims data prior to the index date. Cardiovascular events, healthcare utilization, and its associated costs will be observed from the index date until the end of the study period. Outcomes and the associated costs will be monitored and then compared between cases and controls using inverse probability treatment weighting (IPTW), or, as sample size allows, propensity score matching.

*Monitoring period can also be ended by one of the events described in the data analysis section below

For this study, index date selection period will be from 01/01/2015 to 1/31/2020. Follow-up up period for patients not meeting any of the stopping criteria mentioned below will extend until 3/31/2020.

Finally, starting with the initiation of treatment, we observe patient outcomes until one of the following stopping criteria occur:

- discontinuation (defined as a gap in sulfonylurea, empagliflozin, or metformin of >30 days between fills) or switch or addition of a drug in the comparator and/or other antihyperglycemic agents class
- occurrence(s) of an outcome of interest
- nursing home admission
- healthcare plan disenrollment
- end of the study period

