9.3.2 Outcomes

9.3.2.1 Primary outcomes

Primary outcome

• First hospitalization for congestive heart failure (HHF) (we will first analyze this by looking at diagnosis code in any position, we will then run the analysis considering diagnosis coding in either the principal or secondary position).

The primary scope of the analysis will be limited to the primary outcome (hospitalization for HF), for which the study will be powered for, and limited to HCRU and cost outcomes. For all exploratory effectiveness outcomes outlined above, we will first examine the number of events, and incidence rate of the events in the follow-up for the unmatched cohort, before performing the final analysis, to evaluate feasibility of inclusion of these exploratory outcomes.

Clinical outcomes will be identified by occurrence of a combination of the ICD 9/10 for the respective condition and HCSPCS code. See additional workbooks "ICD 9 Dx Codes.xlsx" and "ICD 10 Dx Codes.xlsx" and "HCPSC codes.xlsx" for a detailed list of relevant ICD 9/10 codes and HCSPCS codes, respectively.

Effectiveness Outcome	Metformin + Sulfonylurea(IR)	Metformin + Empagliflozin (IR)	Hazard Ratio (95% CI)
HHF			
MACE			
Myocardial infarction			
Stroke			
Coronary revascularization			
All-cause death			

See sample results for the propensity score-matched population below:

Utilization Outcome (12 months post index date)	Metformin + Sulfonylurea (IR)	Metformin + Empagliflozin (IR)	Coefficient (95% CI)	P value
Hospitalizations				
LOS				
ED visits				
Outpatient visits				
Drug orders				
Total care costs				
Medical costs				

Pharmacy costs		
2		

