9.3.2.2 Secondary outcomes

Secondary outcomes

- Healthcare utilization outcomes: hospitalizations, emergency department (ED) visits, length of stay, number of filled drugs, outpatient visits
- All cause cost: Total cost of care, divided by medical (inpatient costs, outpatient costs, emergency costs) and pharmacy costs (all reported in Per Patient Per Month (PPPM) costs)

Exploratory outcomes

• Effectiveness outcomes: 2-point MACE as a Composite Score of myocardial infarction, stroke or coronary revascularization

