9.4 DATA SOURCES

This study will utilize IQVIA's Real-World Data (RWD) Adjudicated Claims Database (formerly known as PharMetrics Plus). IQVIA's claims database is composed of more than 190 million unique enrollees from national and sub-national health plans and self-insured employer groups from 2006 to the present.¹⁵ The database is considered representative of the sex and age demographics of the insured United States population.¹⁶ The database contains a multitude of patient data points that are relevant for this study including:

- Demographic, geographic, and insurance type/enrollment information,
- Primary and specialty care visit dates and diagnosis codes,
- Medication use including refill dates, quantity, and days supplied, and
- Hospitalizations and emergency department visit dates, length of stay, and diagnosis codes

We anticipate having access to claims data that was generated though at least December 31, 2019. IQVIA's database has been extensively used in pharmacoepidemiological research. Recent examples include *Pandya et al.* (2020) and *Stolshek et al.* (2018).^{16,17} The claims data will be fully de-identified prior to receiving access for analyses.

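### The shared stopping list ends follow-up at an outcome of interest without limiting this to time-to-event analyses, so as written it also cuts off utilisation and cost follow-up at an event

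*Protocol*

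**What the plan says.** Protocol 9.1 introduces the list for outcomes in general: "starting with the initiation of treatment, we observe patient outcomes until one of the following stopping criteria occur". The second item is "occurrence(s) of an outcome of interest". The others are discontinuation, switch or add-on, nursing home admission, disenrolment and end of study. Section 9.7.1 repeats the outcome item at its head. Step 3 of that section then sets out the Cox model for HHF, the Poisson or negative binomial models for utilisation and the Gamma model for cost.

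Four other statements bear on how long utilisation and cost are followed:

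- 9.1 says: "Cardiovascular events, healthcare utilization, and its associated costs will be observed from the index date until the end of the study period". A footnote there qualifies it: "Monitoring period can also be ended by one of the events described in the data analysis section below". It makes no exception for utilisation or cost.
- 9.3.2.1 gives a results shell for utilisation and cost over the 12 months after index.
- 9.3.2.2 lists "Healthcare utilization outcomes: hospitalizations, emergency department (ED) visits, length of stay, number of filled drugs, outpatient visits", plus all-cause costs per patient per month (PPPM).
- 9.7.1, Step 3, models utilisation as counts.

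In the same 9.1 list, discontinuation is "defined as a gap in sulfonylurea, empagliflozin, or metformin of >30 days between fills". Section 9.4 says the database holds "Medication use including refill dates, quantity, and days supplied".

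**The concern.** Ending follow-up at the event is right for time to first HHF. It is wrong for an outcome that accumulates. Admissions, visits, hospital days and costs continue after a first HHF, and utilisation and cost are the protocol's secondary objectives.

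If their follow-up ends at HHF, the weeks and months after the admission drop out for exactly the patients in whom the treatments are expected to differ. More patients drop out in the arm with more events, so the truncation depends on both outcome and arm. Two programmers could follow the present text and produce different secondary results.

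**Working it through.** **1. The plan's own figures.** Inputs from 9.5: hazard ratio 0.65, two-sided 5% level, 80% power, control share 0.5, 0.8 or 0.9.

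Events = (1.96 + 0.842)² / [(ln 0.65)² × q0 × q1], where (1.96 + 0.842)² = 7.851 and (ln 0.65)² = 0.1856.

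| Control share | q0 × q1 | Computed | Stated |
|---|---|---|---|
| 0.5 | 0.25 | 169.2 | 169 |
| 0.8 | 0.16 | 264.4 | 265 |
| 0.9 | 0.09 | 470.1 | 470 |

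Patient-years at 80% control: 264.4 / 0.01348 ≈ 19,600, as stated (265 / 0.01348 = 19,659). The figures reproduce with 1.96; the 0.96 printed in 9.5 looks like a misprint and is a separate matter. They concern time to first HHF, and an outcome-specific stop leaves them as they are.

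**2. The readings of the outcome item, side by side.**

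| Meaning given to the item | HHF analysis | Utilisation and cost |
|---|---|---|
| Clinical outcomes | Ends at HHF, possibly also at MI, stroke or revascularisation | End at the first such event; later use and cost lost |
| The outcome being analysed | Ends at HHF, as it should | Each count ends at its first occurrence; no clear meaning for cost |
| Any listed outcome | Ends at the first visit, admission or fill | End at the first visit, admission or fill |

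No row leaves utilisation and cost whole. Each conflicts with follow-up to the end of the study period, the 12-month shell, PPPM all-cause costs and count regression. The 9.1 footnote does not resolve this, because it lets the listed events shorten monitoring and exempts nothing.

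**3. Size if the stop is the first HHF.** Rates from 9.5, which takes them from the cited cardiovascular outcome trial of empagliflozin: 14.5 (placebo, assumed for sulfonylurea) and 9.4 per 1,000 patient-years. Assume constant hazards and no other reason for stopping.

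Share cut within 12 months = 1 − e^(−r):

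- Sulfonylurea: 1 − e^(−0.0145) = 1.44%
- Empagliflozin: 1 − e^(−0.0094) = 0.94%
- Ratio: 1.44 / 0.94 ≈ 1.5

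Follow-up lost per patient = 12 × [1 − (1 − e^(−r))/r] months:

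- Sulfonylurea: 12 × (1 − 0.9928) = 0.087 months, or 0.72% of the window
- Empagliflozin: 12 × (1 − 0.9953) = 0.056 months, or 0.47% of the window

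The lost time is a small share of the total. It averages about six months per patient cut (0.087 / 0.0144) and lies entirely after an HHF admission. The protocol gives no cost per admission or per month after HHF, so the effect on PPPM cost cannot be put in dollars. Its direction is open too. Dropping costly months lowers PPPM, while counting the admission and then stopping divides it by fewer months and can raise that patient's PPPM.

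**4. Scale of two stronger literal readings (assumed rates, not from the protocol).**

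- *Stop at any visit*, at 1, 4 or 12 visits a year: mean observed time in a 12-month window, 12 × (1 − e^(−r))/r, is 7.6, 2.9 or 1.0 months.
- *Stop HHF follow-up at MI, stroke or revascularisation*, at m = 0.02 to 0.10 per year, with h = 0.01348. The share of HHF events kept is [h/(h+m)] × [1 − e^(−(h+m)T)] / [1 − e^(−hT)]. This is 99.0% to 95.2% at one year and 98.0% to 90.7% at two. Power from 265 planned events falls from 80.1% to between 79.7% and 76.1%. The calculation assumes independent stopping times, so it measures lost events and not bias.

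**The case against.** The strongest reply is that the authors meant an ordinary time-to-event rule. In Step 3 of 9.7.1 the phrase about an outcome of interest is attached to the Cox model. The 12-month shell, count models and PPPM costs all presuppose follow-up past a first event. An analysis plan, due for completion in June 2021 under section 6, could say so. As an account of intent this stands. It does not remove the defect, because the protocol states the rule twice, places it over all three kinds of model, and confirms in the footnote that it can shorten monitoring.

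Four stronger conclusions are tempting, and the documents do not support them:

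- *Admission and visit counts can only be 0 or 1.* This follows only if the item is taken to cover the utilisation outcome itself. The rest of the protocol shows that this was not intended.
- *The cost offset from avoided HHF is zero by design.* The protocol does not say whether the admission that ends follow-up is counted. It may be, with only later costs lost.
- *HHF is censored at MI or stroke.* No passage says so, and an outcome-specific reading avoids it. The composite of MI, stroke or revascularisation is exploratory and depends on a feasibility check. Under the assumed rates the power loss is at most about four points.
- *Patients on 60- or 90-day fills are all classed as discontinued.* A gap in a drug between fills can reasonably mean days without supply, and days supplied are recorded. The wording can be misread, but it does not impose that result.

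**Conclusion.** The point holds for utilisation and cost. The outcome item in 9.1 and 9.7.1 is not limited to time-to-event analyses, and applied as written it truncates the secondary outcomes at an event. That contradicts the protocol's own observation period, results shell, cost definition and count models.

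If the stop is the first HHF, about 1.4% of sulfonylurea and 0.9% of empagliflozin patients are cut within 12 months. This rests on the 9.5 rates applying here, constant hazards and no other stopping. Discontinuation would lower both shares. A sulfonylurea rate above 14.5, which 9.5 allows for, would raise the first. That the lost period is costly is likely but not quantified in the protocol. The primary HHF analysis is sound provided the stop is read as specific to that outcome, which the text should say. The wording of the refill gap is a minor clarification. The contradiction should be resolved before the analyses are run.

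**What to change.** In 9.1 and 9.7.1:

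1. Apply the outcome stop only to the time-to-event analysis of that same outcome: HHF for the HHF analysis, the first component for the MACE composite.
2. For utilisation and cost, remove the outcome item, so that follow-up continues through and past clinical events to the remaining stopping criteria.
3. Reconcile that period with the 12-month shell in 9.3.2.1. State whether the reported window is 12 months, all available follow-up, or both, and how PPPM treats patients with shorter follow-up.
4. As a secondary wording point, state that the gap of more than 30 days is counted from the end of the days' supply of the last fill.

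The cost is a few sentences in two sections and minor programming. No new data are needed, and the event and patient-year figures in 9.5 do not change.

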9.2 SETTING

N/A

9.2.1 Study sites

N/A

9.2.2 Study population

Inclusion criteria:

- Prevalent metformin use + initiation of empagliflozin OR prevalent metformin use + initiation of a sulfonylurea
- ≥ 18 years of age at index date during study observation
- ≥1 inpatient and/or ≥ 2 outpatient claims denoting T2D diagnosis (in any position) in the 12 months prior to index date (Diagnosis codes available in the appendix Error! Reference source not found.)
- ≥1 inpatient and/or ≥2 outpatient claims denoting CVD (in any position) diagnosis in the 12 months prior to index date (Diagnosis codes available in the additional workbooks "ICD 9 Dx Codes.xlsx" and "ICD 10 Dx Codes.xlsx")
- ≥ 2 months post-index date
- ≥12 months of no exposure to T2D medications in the pre-index period (excluding metformin in both arms)
- ≥ 12 months of continuous enrollment prior to index date

Exclusion criteria:

- Diagnosis of Type 1 Diabetes, secondary, or gestational diabetes in the 12 months prior to index date (Diagnosis codes available in the additional workbooks "ICD 9 Dx Codes.xlsx" and "ICD 10 Dx Codes.xlsx"))
- Diagnosis of severe comorbidities including malignancy, end-stage renal disease, human immunodeficiency virus, Hepatitis C infection, or organ transplant in the 12 months prior to index date (Diagnosis codes available in the additional workbooks "ICD 9 Dx Codes.xlsx" and "ICD 10 Dx Codes.xlsx")
- Admission to nursing home in the 12 months prior to index date

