insulins).⁷ These costs differences were largely due to lower all-cause medical costs, with there being only a small (\$31) cost difference between empagliflozin and other AHA pharmacy costs.⁷ This is significant, as the economic cost of diabetes in the United States was estimated at \$237 billion in annual direct costs in 2017, and patients with diabetes have medical expenditures over twice as high as those without diabetes.^{8,9}

Sulfonylureas are a class of antidiabetic medications which work by stimulating insulin release from pancreatic cells, and include the generics chlorpopamide, glyburide, tolazamide, and tolbutamide.¹⁰ There is some evidence suggesting that sulfonylureas are associated with increased risk of cardiovascular events and mortality. In a review of observational studies comparing metformin and sulfonylureas, the relative risk of adverse events was 13% higher in sulfonylureas patients with a ratio of relative risks of 1.13 (95% CI 1.01-1.27), and the relative risk of death was increased by 20% (RRR 1.20, 95% CI 1.07-1.34).¹¹ Of note, a review of the cardiovascular profile of diabetic drugs found multiple studies suggesting a detrimental effect on cardiovascular health in patients treated with sulfonylureas.¹² Direct comparisons of sulfonylureas to empagliflozin are currently not available, but evidence suggests that empagliflozin is well tolerated as add on therapy to patients using metformin plus sulfonylureas.¹³ Comparisons between the cost effectiveness of sulfonylureas and empagliflozin are not currently available, though previous evidence suggests that metformin is more cost effective than sulfonylureas, with one study estimating an increase of \$2,800 over 25 years when glyburdide was used as first line therapy over metformin, while at the same time accumulating 0.17 fewer quality adjusted life year (QALYs).¹⁴

Given the known benefits of empagliflozin in the T2D population and among those with underlying cardiovascular disease, understanding the current patterns of care and outcomes is important to establish the potential value of increasing use and earlier access to empagliflozin in this high-risk population.

This study would also be the first to assess empagliflozin as second-line after metformin versus second-line initiation of sulfonylureas in the United States using the IQVIA commercial claims database to look at clinical and economic outcomes.

8. **RESEARCH QUESTION AND OBJECTIVES**

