9.3 VARIABLES

Exposure cohorts

Treatment with empagliflozin (as add-on therapy with metformin)

• Treatment with a sulfonylurea (as add-on therapy with metformin) Exposure will be identified by recorded prescription filling matching the NDC codes for empagliflozin or sulfonylurea, respectively. See list of identifying NDC codes in the additional workbook titled "NDC Codes.xlsx".

Covariates

Covariates included will be those previously published in the literature.

Baseline characteristics	Metformin + Sulfonylureas (N =)	Metformin + Empagliflozin (N =)	St. Diff.
Age; mean (sd)			
Age categories			
18 - 54; n (%)			
55 - 64; n (%)			
65 - 74; n (%)			
>= 75; n (%)			
Male; n (%)			
Race			
White; n (%)			
Black; n (%)			
Asian; n (%)			
Hispanic; n (%)			
North American Native; n (%)			
Other/Unknown; n (%)			
Region			
Northeast; n (%)			
South; n (%)			
Midwest; n (%)			
West; n (%)			
Quarter and year of cohort entry			
Q3 2014; n (%)			
Q4 2014; n (%)			
Q1 2015; n (%)			
Q2 2015; n (%)			
Q3 2015; n (%)			
Combined comorbidity score; mean (sd)			
No. distinct diagnoses; mean (sd)			
Diabetic nephropathy; n (%)			
Diabetic retinopathy; n (%)			
Diabetes with other ophthalmic conditions or ophtalmic procedures; n (%)			
Diabetic neuropathy; n (%)			
Diabetes with peripheral circulatory disorders; n (%)			

001-MCS-90-118_RD-23 (1.0) / Saved on: 25 Nov 2019

Diabetic Foot: n (%)			
Lower extremity amputation: n (%)			
Skin infections: p (%)			
Skill infections, $n(70)$			
Foot ulcer; n (%)			
Erectile dysfunction; n (%)			
Hypoglycemia ; n (%)			
Hyperglycemia; n (%)			
(%)			
Diabetic ketoacidosis; n (%)			
Hyperosmolar hyperglycemic nonketotic syndrome; n (%)			
Diabetes with unspecified complication; n (%)			
Naive new user; n (%)			
Monotherapy; n (%)			
Dual therapy with metformin; n (%)			
Concomitant initiation or current use of metformin; n (%)			
Concomitant initiation or current use of sulfonylureas; n (%)			
Past use of metformin; n (%)			
Past use of sulfonylureas; n (%)			
Past use of insulin; n (%)			
Past use of GLP-1 RAs; n (%)			
Past use of glitazones; n (%)			
Any use of meglitinides; n (%)			
Any use of alpha-glucosidase inhibitors; n (%)			
Lifestyle factors			
Obesity; n (%)			
Overweight; n (%)			
Smoking; n (%)			
Alcohol abuse or dependence; n (%)			
Drug abuse or dependence; n (%)			
Ischemic heart disease; n (%)			
Acute myocardial infarction; n (%)			
Old myocardial infarction; n (%)			
Unstable angina; n (%)			

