Endocrinologist visit within prior 30 days; n (%)		
Endocrinologist visit during prior 31-365 days; n (%)		
No. endocrinologist visits; mean (sd)		
Internal medicine visit within prior 30 days; n (%)		
Internal medicine visit during prior 31-365 days; n (%)		
No. internal medicine visits; mean (sd)		
Cardiologist visit within prior 30 days; n (%)		
Cardiologist visit during prior 31-365 days; n (%)		

No. cardiologist visits; mean (sd)	
Electrocardiogram; n (%)	
No. electrocardiograms, mean (sd)	
No. distinct medication prescriptions; mean (sd)	
Use of glucose test strips; n (%)	
No. HbA1c tests ordered; mean (sd)	
No. glucose tests ordered; mean (sd)	
No. microalbuminuria tests ordered; mean (sd)	
No. creatinine tests ordered; mean (sd)	
No. BUN tests ordered, mean (sd)	
No. lipid tests; mean (sd)	

The table above shows our complete set of baseline characteristics. All comorbidities and previous acute conditions and previous utilization in the previous 12 months will be recorded. Age at index date will be calculated as the time difference between the index date and the patient's birth date. Identification of comorbidities and previous utilization will follow the following rules:

- Chronic comorbidities and previous acute conditions will be identified by occurrence of at least one ICD 9/10 for the respective condition in any position. See the additional workbooks titled "ICD 9 Dx Codes.xlsx" and "ICD 10 Dx Codes.xlsx" for a detailed list of ICD 9/10 codes that identify comorbidities.
- Previous healthcare utilization will be identified by occurrence of CPT or HCPCS codes for the respective form of utilization. See the additional workbooks "CPT codes.xlsx" and "HCSPCS codes.xlsx" for a detailed list of CPT and HCPCS codes.
- Previous prescription medications will be identified by occurrence of prescription filling with a medication's respective NDC or HCSPCS code. See additional workbook "NDC codes.xlsx" and "HCSPCS codes.xlsx" for a detailed list of relevant codes.

Also, given that we are comparing a branded agent against generic agent, we will perform exploratory instrumental variable analysis, in order to account for the confounding by indication. Some example of instrumental variables we can use and will explore the appropriateness of are:

- First three digits of zip code (ZIP3) and/or State
- National Provider Identifier (NPI)
- Index date and/or index quarter

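### The 12-month washout shows no recent use of other diabetes drugs, not second-line status, and it empties the non-metformin past-use covariates that could flag earlier treatment

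*Protocol*

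**What the plan says.** The study title (Protocol, section 4) speaks of 2nd-line initiation after metformin in both arms. Section 7 presents the study as the "first to assess empagliflozin as second-line after metformin versus second-line initiation of sulfonylureas".

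Eligibility is in section 9.2.2. The entry event is "Prevalent metformin use + initiation of empagliflozin" or the same with a sulfonylurea. Drug history is governed by "≥12 months of no exposure to T2D medications in the pre-index period (excluding metformin in both arms"), and observable history by "≥ 12 months of continuous enrollment prior to index date". No criterion requires that metformin be the only earlier glucose-lowering drug.

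For covariates, section 9.1 says: "Baseline characteristics for all patients as well as their enrollment status will be confirmed using 12 months of claims data prior to the index date". Section 9.3 adds: "All comorbidities and previous acute conditions and previous utilization in the previous 12 months will be recorded". The covariate table in 9.3 includes "Past use of sulfonylureas; n" (%) and matching rows for insulin, GLP-1 RAs, glitazones and metformin.

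Section 9.9 names confounding in general and the absence of HbA1c values. It does not mention earlier treatment lines.

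**The concern.** A washout of fixed length shows that a drug was not filled recently. It does not establish line of therapy. Someone who took a sulfonylurea, a DPP-4 inhibitor or insulin, stopped more than 12 months before index, continued on metformin and then started the index drug meets every criterion in 9.2.2 and is analyzed as second-line.

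The past-use rows in the covariate table look like the safeguard. They cannot work as one, because baseline covers the same period that eligibility requires to be free of those drugs.

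This matters more than usual here. With no HbA1c values, treatment history is one of the few markers of diabetes stage that claims can supply. Section 9.3 itself expects confounding by indication, because a branded agent is compared with a generic one. If the arms differ in earlier treatment, the HHF comparison carries a difference in disease stage that the propensity score sees only indirectly, and the second-line label would not describe everyone studied.

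**Working it through.** The plan gives no figure on this point to reproduce. The check compares the two windows, works out the look-back, and illustrates the possible size.

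**1. Eligibility window against covariate window**

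| Item | Window | Source |
|---|---|---|
| No T2D drug except metformin | at least the 12 months before index | 9.2.2 |
| Continuous enrollment | at least the 12 months before index | 9.2.2 |
| Baseline characteristics | the 12 months before index | 9.1 |

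Let X = 1 if a patient filled a given non-metformin antidiabetic drug in the 12 months before index. Eligibility requires X = 0, so P(X = 1 | eligible) = 0 and Var(X | eligible) = 0. A constant carries no information in a propensity model. This applies to the past-use rows for sulfonylureas, insulin, GLP-1 RAs and glitazones. It does not apply to past metformin use, which the washout exempts.

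The 12-month sentence in 9.3 names comorbidities, acute conditions and utilization, and the separate bullet on previous prescriptions gives no window. The result for drug history therefore rests on the general sentence in 9.1.

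**2. Look-back that the data could hold**

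Inputs (9.1): data from 1 January 2014; index dates from 1 January 2015 to 31 January 2020.

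- Indexed 1 January 2015: 12.0 months at most, so nothing beyond the washout.
- Indexed 1 July 2017 (about the middle): 42.0 months at most, 42.0 − 12 = 30.0 beyond the washout.
- Indexed 31 January 2020: 73.0 months at most, 73.0 − 12 = 61.0 beyond the washout.

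These are calendar ceilings. Only 12 months of enrollment is required, and the Protocol gives no enrollment durations, so the look-back actually observed may be much shorter.

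**3. Illustration of size (shares and risk ratios assumed)**

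Let p1 and p0 be the shares with earlier non-metformin treatment in the empagliflozin and sulfonylurea arms, and k their HHF risk ratio against true second-line patients. With no adjustment through other covariates,

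bias factor = [1 + p1(k − 1)] / [1 + p0(k − 1)].

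Applied to the hazard ratio of 0.65 planned in 9.5:

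| p1 | p0 | k | Factor | 0.65 becomes |
|---|---|---|---|---|
| 10% | 5% | 1.3 | 1.03/1.015 = 1.015 | 0.66 |
| 20% | 5% | 1.5 | 1.10/1.025 = 1.073 | 0.70 |
| 30% | 5% | 2.0 | 1.30/1.05 = 1.238 | 0.80 |
| equal | equal | any | 1.000 | 0.65 |
| 5% | 20% | 1.5 | 1.025/1.10 = 0.932 | 0.61 |
| 5% | 30% | 2.0 | 1.05/1.30 = 0.808 | 0.53 |

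The direction depends entirely on which arm has more such patients.

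**The case against.** The strongest reply is that the formal objective in section 8, and the design and exposure sections, speak of add-on therapy to metformin, which the eligibility rule delivers. A fixed, equal 12-month washout is also a defensible new-user design. Both points stand. They make the mismatch one between the title and rationale on one side and the cohort on the other. They do not explain why the table lists covariates that cannot vary.

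Four stronger readings are tempting, and the Protocol does not support them:

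- *Earlier treatment cannot be adjusted for at all.* The Abstract lists length of metformin use. The table in 9.3 lists diabetic complications, endocrinologist visits, HbA1c tests ordered and number of distinct prescriptions. These are partial proxies for stage, though none records earlier use of another agent. The table in the working assumes that they do nothing, so it overstates the bias to the extent that they help.
- *The hazard ratio is pulled toward 1.* This needs earlier treatment to be commoner in the empagliflozin arm. The Protocol gives no share for either arm.
- *Patients who start another agent on the index date contaminate the cohort.* The stopping rules in 9.1 and 9.7.1 end follow-up when another antihyperglycemic is added or taken, so such patients would largely be stopped at or near time zero.
- *One patient can count in both arms.* No once-only rule is stated, but this is a cohort-construction detail that may be set in the analysis plan.

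A last objection is that excluding on all available history has a price. Look-back would differ by enrollment length, which cohort-entry quarter cannot fully absorb. The preliminary count in 9.5 has 2,550 empagliflozin patients, 582 of them without metformin, leaving 2,550 − 582 = 1,968. This stands, and it favors a flag and a sensitivity analysis over mandatory exclusion.

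**Conclusion.** The point holds. Eligibility supports a cohort of new users after a 12-month washout on metformin. It does not support the second-line label in the title and rationale. Under the baseline window in 9.1, the past-use rows for sulfonylureas, insulin, GLP-1 RAs and glitazones are zero for every eligible patient, which follows from the two rules without any assumption.

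The effect on the result is not established. Under the assumed shares (5% to 30%) and risk ratios (1.3 to 2.0), a true hazard ratio of 0.65 could appear anywhere from about 0.53 to 0.80, and with equal shares it would not move. That unknown can be partly measured in data already held, so the plan should be changed, but the point does not invalidate the main analysis.

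**What to change.** 1. **Section 9.3:** define the non-metformin past-use rows over all available pre-index data, from 1 January 2014 with a minimum of 12 months, and flag any earlier use. Report the flag by arm together with the length of look-back.
2. **Section 9.7.2:** add an HHF sensitivity analysis restricted to patients with no non-metformin antidiabetic claim in that look-back, ideally among those with longer pre-index enrollment.
3. **Section 9.9:** state that the main cohort is new users after a 12-month washout, and that earlier treatment lines cannot be ruled out.

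The cost is wording and programming on data already held, and no patient leaves the main analysis. Look-back will vary with enrollment and index date, so an unflagged patient with short history is not known to be second-line. Patients indexed in early 2015 gain almost nothing. The restricted analysis will be less precise.
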